The research team has strict and secure procedures for protecting against and minimizing potential risks to human subjects' data. All survey data will be entered directly into REDCap, a password-protected database managed by the Center for Research Informatics (CRI) at the University of Chicago (cri.uchicago.edu). CRI provides a HIPAA-compliant data storage and computing environment that has achieved security accreditation by the Biological Sciences Division's Risk Management Group. Data will be saved to the secure servers at the University of Chicago via a secure wireless connection on a secure, password-protected tablet, or research

staff will enter REDCap data directly on departmental computers using the secure, password-protected network. Data are backed up at the end of each collection day. Data will never be stored locally.

We will use Mosio, a text messaging platform, to facilitate the text message protocol for human subjects in the intervention group and manage survey scheduling and reminders for all participants. To this end, REDCap will retain certain data elements to Mosio via REDCap's secure API. Mosio provides a secure messaging and data storage environment and has been approved for use by the University of Chicago Information Security Office. Only approved researchers on the study team will have access to data stored by Mosio and will have the ability to securely download data directly to password-protected computers.

REDCap will integrate electronically with NowPow (www.nowpow.com) to facilitate generation of the HealtheRx. Data will be pushed from REDCap to NowPow via a custom secure integration to create the participant's profile in NowPow, including name, address, date of birth and other non-PHI data. Any data sent to NowPow from REDCap to generate the personalized HealtheRx will be assigned a secondary unique ID in order to prevent any connection to the subjects' responses in REDCap. NowPow is seamless, secure and HIPAA-compliant. Data are backed up automatically and encrypted in-transit, at-rest, and end-to-end. De-identified metadata will be transferred to researchers in the [name] Laboratory using the Globus system; details described above. All devices used by researchers to collect or access research files will be encrypted. Only approved research analysts will have access to files that link participant's PHI to their unique identifiers for the purposes of creating analytic datasets.

REDCap will integrate electronically with the Mosio texting platform (www.mosio.com) to facilitate the text message protocol for human subjects in the intervention group and manage survey scheduling and reminders for all participants. To this end, REDCap will push the subject's name, telephone number and date of enrollment to Mosio via REDCap's secure API. Mosio provides a secure messaging and data storage environment and has been approved for use by the University of Chicago Information Security Office. Only approved researchers on the study team will have access to data stored by Mosio and will have the ability to securely download data directly to computers within the UCM network.

All hard copies of project materials will be stored in locked file cabinets in locked offices at University of Chicago. Laptop computers used to collect data will be encrypted and password protected. All data transmitted to secure servers will be encrypted. Analytic files will either be de-identified prior to analysis or limited to the minimum amount of data necessary to accomplish the intended research purposes per the HIPAA Privacy Rule. Any analytic datasets will limit the use or disclosure of PHI to the minimum necessary, if any at all, to accomplish the intended research purposes. Only IRB-approved researchers on this protocol will have access to data. These controls meet or exceed the strictness of practices legislated and enforced by the University of Chicago Biological Sciences Division and hospitals for protected health information.

Procedures are in place to ensure confidentiality and provide informed consent as discussed above. Numeric coding of surveys/interviews and secure containment of files that link participant's responses from PHI will also minimize this risk. Finally, the research team will provide a contact phone number that will be included on all study correspondence and forms. The purpose of this phone number is to provide respondents with a single number to call if they have questions about any aspect of the study.

O. Bibliography (please refer to the end of the document)

P. Recruiting methods

Given the shift to telehealth appointments at UCM and shelter-in-place orders due to the COVID-19 pandemic, we are planning to conduct this study completely remotely. We will also work with CRI to create an ACRES Report to obtain a list of eligible patients. Researchers will contact patients by phone and explain that patients may be eligible for a research study and screen patients for eligibility if the patient is interested. If the patient is eligible, researchers will send them an e-consent form using REDCap that is able to be filled out online or other methods described earlier. The e-consent process is one that has been developed successfully in our lab.

[name] and [name] lead the My Diabetes, My Community trial - a three-arm parallel pragmatic randomized controlled trial among older, predominantly African American patients with type 2 diabetes seen at the University of Chicago. A dementia diagnosis and inability to complete the study on their own are two of the exclusion criteria for the trial. During screening, it is possible for research assistants to contact patients living with dementia or their caregivers. When a patient with dementia and their caregiver are identified and screen out in the MDMC trial, there is an opportunity to ask whether they would be interested in participating in another trial they may be eligible for - the CommunityRx-Caregiver trial. The MDMC research assistant would ask if the patient is interested in hearing more about a trial they may be eligible for and whether it is ok to share their phone number with the CommunityRx-Caregiver team. In receiving verbal consent to share their phone number with the CommunityRx-Caregiver team, the MDMC research assistant will document this in the patients' screening data in REDCap and notify the MDMC Project Manager (PM). The MDMC PM will then flag this record to the CommunityRx-Caregiver PM. [name], who is also on the MDMC staff. A CommunityRx-Caregiver team member will then follow-up with the patient about participating in the CommunityRx-Caregiver study.

If we are able to safely approach patients in-person again, as we have done in prior trials in this setting, we will review the informed consent and study procedures with them.

In addition to recruiting via ACRES reports and CRI data mart, we will use the ITMs research profile website, <https://betheenewnormal.org/>, and researchmatch.org to post our study and to use it as a recruiting tool for eligible subjects.

Once their participation in the RCT is complete, a purposeful sample of participants will be approached for inclusion in a focus group. Researchers will contact participants by email, text message and phone. In order to appropriately capture data relative to each study arm, we will purposefully recruit participants based on study arm.

Research interviewers will explain that the participant may be eligible for a research study and, if interested, further screen for eligibility. Recruitment scripts for the various modes of contact have been submitted for review with this protocol. If eligible, researchers will guide participants through the informed consent process as described in Section M. Informed Consent.

Q. Notification of physician

Notification of the subject's treating physician for permission to enroll will occur using a multi-pronged approach. First, we will educate all treating physicians and residents working in the target clinics about the study prior to study enrollment and give treating physicians (along with their patients) the opportunity to opt out of study participation. Secondly, we will use these

education sessions to identify how treating physicians wish to be contacted for permission (e.g., via text, email, phone, text page or through the electronic medical record system). We will use that communication as documentation of treating physician permission.

R. Anticipated coordination

Inter-departmental faculty coordination will be facilitated by regular research meetings attended by Drs. and [name] (PIs) and other Co-Investigators and key personnel. Faculty will also regularly communicate by email and phone calls as necessary. Co-Principal Investigator [name] (Professor of Medicine) will oversee enrollment of subjects in the Primary Care Clinic and the University of Chicago PBRN Clinics (<https://pbrn.uchicago.edu/>).

S. Pregnancy test

Not applicable.

T. Exclusion of women, minorities and/or children

This study will not exclude women, minorities or children.

U. Drugs

No drugs will be given to subjects as part of this study.

References

REFERENCES

1. [name] ES, Laiteerapong N, Liu JY, John PM, Moffet HH, Karter AJ. Rates of complications and mortality in older patients with diabetes mellitus: the diabetes and aging study. *JAMA Intern Med.* Feb 1 2014;174(2):251-258.

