Electronic Health records will be a critical source of data on key processes of care that are affected by My Diabetes GOAL including goal setting measures (documenting personalized goals of diabetes care, proportion following ADA recommendations, proportion choosing alternative goals) as well as referrals to care management and frequency of phone contacts. The EHR will also be the primary source of data for risk factor levels (glycosylated hemoglobin, blood pressure, cholesterol levels), medications, and health care utilization (outpatient visits, care management services, ER visits, and hospitalizations). These data are continually collected as a part of routine care. If participants receive care outside of the UChicago system during the duration of the study and their most recent A1C is not available in the EMR via Care Everywhere, we will ask the participant to self-report the A1C and offer the option for them to securely upload their results via REDCap survey link to be stored with the rest of their study data. Previously consented subjects that receive care outside of UChicago Medicine will be resent the original signed informed consent for review and asked to complete an addendum to the consent to include this upload option. All future subjects will have this upload option included in an updated informed consent. We will ask subjects for permission to access their medical records for these purposes.

Subjects will be randomized in a 1:1:1 ratio to the attention control, MDG, or MDG+CRx groups. All subjects will be asked to complete surveys upon enrollment, at 6 months, and 12 months. This will be a single-blind study, and subjects will be blinded to the different groups.

My Diabetes, My Community Study Protocol

09/16/2024

Attention control Arm: These subjects will receive monthly calls with a member of the study team.

My Diabetes GOAL Arm: Subjects will be asked to complete a survey, complete goal setting conversation with diabetes nurse, and monthly telephonic care management calls. Care management calls include review of 1) risk assessment and treatment preferences, 2) goal setting discussion 3) medication management, and referrals to hospital-based services such as diabetes education classes.

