Usual care for diabetes at the University of Chicago is constantly evolving and has features that are important to describe and acknowledge. Since 2018, [name] has been co-chair for diabetes quality improvement at University of Chicago Medicine. University of Chicago has high rates of poor diabetes control based on the quality measure of A1C>9.0%. To reduce rates of poor control, the ambulatory quality improvement team has: 1) conducted system wide outreach to patients to get an A1C test, 2) installed Best Practice Alerts to remind physicians to order lab tests for diabetes, 3) installed point of care testing to primary care clinics, 4) created new drug prescribing SmartSet modules, and 5) organized and vetted patient education materials. University of Chicago also has diabetes education programs, a specialized pharmacist designated to solve problems with high drug prices. This collection of interventions has been associated with steady decline in the rates of poor control (29.2% in April 2019 to 26.6% in March of 2020).

To reduce the chance that benefits from the My Diabetes GOAL arms are due to attention alone, we will also conduct monthly calls to attention control subjects but will not discuss specific issues related to diabetes care. These calls will also help to ensure retention of attention control subjects in the study.

To reduce bias, we will blind participants to the arm of the intervention at the time of enrollment.

H. Type and number of experimental subjects

Individuals will be contacted for enrollment using methods described below in Section P. Recruiting Methods. Individuals will be contacted, screened for inclusion, recruited for study participation and participate in the informed consent process. We plan to enroll up 517 patients (12 in the pilot, 505 in the RCT). We will determine trial arm assignment through a random number generator. Patients will be blinded to study hypotheses and will be unaware of allocation. Our data analyst will be blinded to the treatment allocation of patients.

Inclusion Criteria:

- Males and females 60 years of age or older
- A1C 7.5% or greater
- Clinical encounter at UChicago practice in prior year
- Have access to a cell phone and provides the research interviewer with the cell phone number with internet access OR have a personal email address.

Exclusion Criteria:

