Aims 2 and 3: To compare self-care continuous outcomes and clinical continuous outcomes including A1C (primary outcome) over the three study groups, a repeated measure analysis of variance via LMM will be performed to model one outcome over time and test the effects of treatment, time and their interaction. Clinic will be considered as random effects in a LMM to account for within-site association. We will fit an unadjusted model first and then an adjusted model adjusting for baseline outcome and participant-level potential confounders as mentioned above. Normality will be checked and appropriate data transformation will be performed if data highly skewed. The p-value for the group comparison between MDG and MDG+CRx in A1C at 12 months will be used for the primary objective analysis at the two-sided significance level of 5% (consistent to the power justification (below)). Multiple pairwise comparisons will be conducted to compare between groups at each time point and compare the multiple time points within a group. All the multiple comparisons and analyses of all the secondary outcomes will be considered to be exploratory and will not spend the overall type I error rate of 5%. To compare each of binary outcomes such as utilization of community-based resources, we will use GEE and GLMM for group comparisons, as mentioned in analyses of Aim 1. To compare health care use (ED and hospitalizations), we will use both Poisson and negative binomial regression models. If the health care use data are zero-inflated (i.e., >50% of patients who have no service use), we will use both zero-inflated Poisson and zero-inflated negative binomial models.

Sensitivity analyses: We will also assess the impact of our interventions across patient subgroups (age group, health status, baseline A1C group, and diabetes duration with different thresholds).

Interim analyses: We will apply the statistical methods above to all the available data including baseline, all 6-month follow-up data, and about 75% 12-month follow-up data.

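### The outside-care fallback for the primary 12-month A1C accepts an undated value, and no month-12 window is stated for either data source

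*Combined protocol and SAP*

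**What the plan says.** Section I, Aims 2 and 3, fixes the primary analysis: "The p-value for the group comparison between MDG and MDG+CRx in A1C at 12 months will be used for the primary objective analysis".

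Section C describes where A1C comes from: "The EHR will also be the primary source of data for risk factor levels (glycosylated hemoglobin, blood pressure, cholesterol levels". It adds: "These data are continually collected as a part of routine care". Table 1 lists the A1C source as EHR or survey. The scheduled study assessments are questionnaires: "All subjects will be asked to complete surveys upon enrollment, at 6 months, and 12 months". No section orders an A1C at any of these times.

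The fallback, also in Section C, has two conditions. The first is outside care: "If participants receive care outside of the UChicago system during the duration of the study". The second, with the resulting action, is that "their most recent A1C is not available in the EMR via Care Everywhere, we will ask the participant to self-report the A1C". Participants may also upload the result through a REDCap link. The text sets no earliest acceptable date and does not ask for the date of the test.

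Section I, under the added usual care arm, reports that by May 2024, 133 of the 167 attention-control patients had an EHR A1C at the 12-month point. It does not say what qualified a test as a 12-month result.

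**The concern.** The planned mixed model tests treatment, time and their interaction, and compares groups at each time point. Routine A1C tests fall on irregular dates, so each must be assigned to a time point before the model can be fitted. That assignment is part of the definition of the primary outcome, and the plan does not give it.

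The gap matters most in the fallback. An EHR result normally carries a date, so an analyst can still apply a window to it. A self-reported value collected as Section C describes need carry none. If the participant's latest test was at month 4, that figure can be recorded with the 12-month survey, and nobody could later screen it out. Values taken before the intervention has had its full effect pull the MDG versus MDG+CRx difference toward zero.

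The missing window has a second consequence. The March 2024 interim analysis included A1C, and attention-control A1C results were in hand by May 2024. A window first written down after that is open to the criticism that it was chosen with results known.

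**Working it through.** **1. The plan's own figures.** Availability in attention control: 133/167 = 79.6%, so 34/167 = 20.4% had no 12-month EHR A1C.

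The only sample-size calculation in the documents is for usual care versus attention control (difference 0.97, SD 1.64, two-sided 5%). With 39 versus 133 patients, SE = 1.64 × √(1/39 + 1/133) = 0.299, and power = Φ(0.97/0.299 − 1.96) = 90.1% (89.8% with the noncentral t). Allowing for 20% attrition, 39/0.8 = 48.75, so 49. Both stated figures are reproduced. I borrow only the SD below. No effect size or sample size is given for MDG versus MDG+CRx.

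**2. Does 133/167 imply a date criterion?** Entry required an A1C of 7.5% or greater, so every participant had at least one A1C. If any value of any date counted, almost nobody would be without one. Since 34 were, some criterion was applied to EHR values, and it at least shut out the entry value. Its width is not stated.

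**3. Ceiling on the affected share.** The fallback reaches only participants with outside care and no value in Care Everywhere. In attention control these lie among the 34, so f ≤ 20.4%. The true share is probably smaller. The 34 also include anyone lost to follow-up and, because recruitment ran to 07-07-2023 and the count was made by May 2024, anyone not yet at month 12. The counts for the two primary arms are not given; I assume they are similar.

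**4. Dilution of the primary contrast.** Let a share f of 12-month values in each arm be early and carry a fraction g of the month-12 effect. The expected difference is multiplied by 1 − f(1 − g).

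| f | g = 0.5 | g = 0 |
|---|---|---|
| 10% | 0.95 | 0.90 |
| 20.4% | 0.90 | 0.80 |

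If the effect builds linearly, g = 0.5 corresponds to a test at month 6.

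**5. Illustrative power.** Assume SD 1.64 and 133 analysed per arm, so SE = 1.64 × √(2/133) = 0.201. The difference giving 80% power is (1.96 + 0.84) × 0.201 = 0.563. Power = Φ(difference/SE − 1.96).

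- If 133 per arm are analysed and a share of them is early: for f = 10%, power is 75.9% (g = 0.5) or 71.3% (g = 0); for f = 20%, 71.3% or 61.1%.
- If 34 early values are added to 133 valid ones: n = 167, SE = 1.64 × √(2/167) = 0.179. With g = 0.5, 0.563 × 0.898 = 0.506 and power is about 80.5%. With g = 0, 0.563 × 0.796 = 0.449 and power is about 70.5%.

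In the second case, accepting early values that carry half the effect costs essentially no power compared with leaving them missing. The estimate is still about 10% too small. The firm loss is therefore in the estimate; the loss of power depends on how stale the values are.

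**6. Comparisons with attention control.** Section G provides for "monthly calls to attention control subjects but will not discuss specific issues related to diabetes care", while the MDG arms have monthly nurse calls, so test timing could differ. If attention-control values were on average 2 months earlier and the 0.97 fall were linear over 12 months, the spurious difference would be 0.97 × 2/12 = 0.16. This is an illustration only: neither the 2-month gap nor linearity comes from the documents.

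**The case against.** The strongest reply is that outcomes from routine records are a legitimate choice in a pragmatic trial planned as fully remote, and that the phrase about the most recent A1C only says when staff should ask a participant. It does not say that the answer becomes the 12-month outcome. The 133/167 count shows that a date criterion was in use. Section I makes observed data the main analysis and imputation a sensitivity analysis, which fits leaving absent values missing. Most of this stands. The lack of a study-ordered A1C is not itself a defect, and for EHR values alone the unstated window is close to a missing detail.

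Three stronger readings are tempting and are not supported:

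- A reader might infer that the latest value of any date is used for everyone, so that an entry A1C could be carried forward as follow-up. The wording governs only outside-care participants whose value is not in Care Everywhere, and the 133/167 count is inconsistent with such a rule for EHR values.
- A reader might infer that different test timing biases the primary test. Both primary arms have the same monthly nurse calls. The argument applies to comparisons with attention control, which Section I classes as exploratory, and Section G describes A1C outreach and physician alerts that are not specific to any arm.
- A reader might infer that A1C fell over time in every arm. A change is reported for attention control only. Because patients were selected for a raised A1C, part of that fall could be regression to the mean, already present at the first retest. A 2-month gap would then produce less than 0.16.

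The reply leaves one thing unanswered: nothing in the plan stops an undated, self-reported value from being used as the 12-month outcome.

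**Conclusion.** The concern holds for the fallback and, more weakly, for the unstated EHR window. As written, Section C can admit an A1C from well before month 12 into the primary outcome without a date by which to exclude it. The direction is dilution of the MDG versus MDG+CRx difference. The size is unknown. Using the attention-control ceiling, it is at most about 10% if early values carry half the effect and about 20% if they carry none. This assumes that the primary arms resemble attention control, that early values are equally common in both, and that all who lacked an EHR value entered through the fallback. The true figure is likely to be smaller. The 0.16 timing figure does not bear on the primary test. The change should be made before the final analysis, since it is specific and inexpensive.

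**What to change.** 1. Require the test date for every self-reported or uploaded A1C, and ask for the result nearest month 12 instead of the latest one.
2. State one month-12 window, counted from randomization, for all arms and both sources. Preferably use the rule already applied for the 133/167 count, and disclose it, because a new window would follow the interim A1C analysis. If no such rule can be documented, an example is the test closest to day 365 within about 3 months either side (days 274 to 456), with no test used for two time points.
3. Treat undated or out-of-window values as missing in the main observed-data analysis.
4. Run a sensitivity analysis with a narrower window, or with in-window laboratory values only. This is useful because, under linear build-up, a test at month 9 carries only 9/12 = 75% of the month-12 effect.
5. Report, by arm, how many 12-month values came from each source and how many were excluded as undated or out of window.

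The cost is wording in Sections C and I, a date field in REDCap, and a few values becoming missing. With recruitment closed on 07-07-2023, 12-month follow-up should have ended around July 2024. Dates for values already self-reported would have to come from uploaded reports or recontact, and some may not be recoverable.

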MDG + Community Rx Arm: Subjects will receive the same intervention above as well as receive vetted, personalized referrals near the subject's location to human, social and other community-based supports aligned with their diabetes goals and other needs. Beginning with the first monthly telephone care management call, the nurse will launch CommunityRx, enroll the patient, and utilize NowPow to produce a "prescription" HealtheRx that can be printed, delivered by MyChart, text message, and/or e-mail, according to the patient's preference. This will be repeated at each subsequent monthly call.

All participants in the study will receive reminders by phone, e-mail, or MyChart message for scheduling monthly calls and follow-up surveys.

Participants in all three arms will complete a baseline survey (by phone, video or online) and at 6 months and 12 months. Please see Table 1 for list of outcomes and corresponding methods to obtain the data. If needed to supplement healthcare utilization data, we will obtain health insurance claims for the participant. The informed consent process will inform study participants of the rationale for accessing these data and request participants' permission to do so, if needed.

Table 1. Outcomes and Data Collection

Aim	Outcome	Source
Aim 1	Shared decision making questionnaire ^{94,95}	Survey
	Decisional Conflict ⁹⁶	Survey
	Documentation of A1C goal	EHR
	Patient self-report of A1C goal	Survey
Aim 2	Diabetes self-efficacy ⁹⁷	Survey
	Diabetes self-care inventory ⁹⁸	Survey
	Medication adherence	Survey
	Dietary adherence	Survey
	Physical activity adherence ⁹⁹	Survey
	Knowledge and utilization of community-based resources ¹²	Survey / NowPow
Aim 3	Glucose control (A1C)	EHR or Survey
	Hypoglycemia (self-reported) ⁸¹⁻⁸³	Survey
	Hypoglycemia requiring medical assistance	EHR
	Geriatric syndromes	Survey and EHR
	Depression ¹⁰⁰	
	Falls ¹⁰¹	
	Cognitive Impairment ¹⁰²	
	Frailty ¹⁰³	
	Urine Incontinence ¹⁰⁴	
	Polypharmacy	

	Functional status Disability of (Instrumental) Activities of Daily Living ^{105,106} Lower Extremity Strength using 5-Repeated Chair Stands ¹⁰⁷ Gait speed using 8-Foot Usual Walk ¹⁰⁷	Survey
	Quality of life (SF-8) ¹⁰⁸	Survey
	ED visits and unplanned hospitalizations	EHR/Medicare claims

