- Patients unable to provide consent for themselves (specifically with a diagnosis of Alzheimer's disease and related dementias) and complete outcome assessments
- Terminal illness
- Living in an institutional setting (non-community dwelling)
- Unable to read, write, or speak English or Spanish
- Recent enrollment in My Diabetes GOAL or Community Rx Trials

I. Statistical analysis

An intention-to-treat analysis principle will be applied to all patients' outcomes, regardless of ineligibility and actual intervention provided. Multiple imputation will be used to impute missing

values for those data missing at random.¹¹² We will conduct analyses using observed data as main analyses and imputed data as part of sensitivity analyses.

Aim 1: To compare continuous outcomes such as the decisional conflict score, we will use a linear mixed model (LMM) over the three study groups. To compare processes that are binary (e.g., patients self-reporting a goal) at 12 months, a chi-squared test and a logistic regression model will be used and the latter method will adjust for patients' potential confounders such as age, gender, race, health status, and duration of diabetes. In addition, we will use the generalized estimating equations (GEE) and generalized linear mixed model (GLMM) (which may be computationally intensive) to model proportion of patients with documented goal over time (baseline and 12 months) and test the effects of treatment, time, and interaction between treatment and time.

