Qualitative interview data will be systematically collected and analyzed using rapid qualitative methods.¹¹⁷ Rapid qualitative methods are well-suited for mixed methods studies and commonly used in implementation science studies when quick understanding of qualitative data is needed to inform next steps or to help interpret or triangulate findings. Rapid qualitative methods use constant comparison of data to inform continued data collection, and analysis is conducted during data collection through the use of text summaries.

Focus groups will be audio-recorded to ensure the accuracy of participants' responses. Researchers will create a data analysis template that includes a neutral domain name that corresponds with each focus group question. Trained researchers will listen to the audio of each focus group session and create a summary of each domain, with space for other observations that may occur during data collection. Then, all text summaries will be collated into one matrix (focus group x domain) and assessed for similarities and differences across responses and by

domain. Matrices may also be set up by individual focus group or by respondent study arm (e.g., pooling all responses for those who participated in the intervention group), if appropriate. Matrices will be analyzed for gaps in the data, emergent themes and to generate summaries of responses from participants in each study arm.

Addition of a Usual Care Arm

To assess whether the experience of the participants within the trial differs from patients at UCM who did not participate in the trial during the study timeframe, we will include a Usual Care Arm based on the original eligibility criteria used to generate the ACRES recruitment lists of patients and include retrospective outcomes data (A1C and medications between 9-23-2020 to 9-16-2024).

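### Do self-reported A1C values without a laboratory document undermine the primary 12-month comparison?

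*Combined protocol and SAP*

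**What the plan says.** Section C (Methodology) makes the electronic health record the main source of A1C and gives a fallback with two conditions: "If participants receive care outside of the UChicago system during the duration of the study and their most recent A1C is not available" through the record-sharing system. In that case, "we will ask the participant to self-report the A1C and offer the option for them to securely upload their results via REDCap survey link". Outside-care participants who had already consented are "asked to complete an addendum to the consent to include this upload option"; later participants have it in their consent form. Table 1 accordingly gives the A1C source as the record or the survey.

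Section I (Statistical analysis, Aims 2 and 3) names one confirmatory test, two-sided at 5%: "The p-value for the group comparison between MDG and MDG+CRx in A1C at 12 months will be used for the primary objective analysis". All other comparisons are exploratory. On missing data: "We will conduct analyses using observed data as main analyses and imputed data as part of sensitivity analyses". The other analyses labelled as sensitivity are subgroups: "We will also assess the impact of our interventions across patient subgroups", by age, health status, baseline A1C and diabetes duration. None is by A1C source.

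The usual-care addition in Section I will "include retrospective outcomes data (A1C and medications between 9-23-2020 to 9-16-2024") for patients outside the trial. Its sample size rests on the 133 of 167 attention-control patients who had a 12-month A1C in the record.

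**The concern.** A1C is valued as an endpoint because a laboratory produces it. A figure recalled by the participant can be wrong, rounded, or taken from a test on another date. Since upload is optional, an undocumented figure could enter the primary model as observed data on the same footing as a laboratory result. No planned analysis would show a reader whether the result depends on such figures.

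Three effects are possible. Random error would widen the confidence interval of the primary contrast. Error that differs between arms would bias a contrast; this is most plausible against attention control, because patients coached towards an A1C goal may report a figure closer to it. In the usual-care comparison, one side is retrospective record data whose patients cannot self-report, so admitting self-reports on the other side would make the measurement unequal.

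**Working it through.** **Inputs.** From the usual-care addition in Section I: 167 attention-control patients, 133 with a 12-month A1C in the record by May 2024, mean reduction 0.97, SD of change 1.64. The self-reported share is not given. Assumptions: the other two arms resemble attention control in size, SD and record coverage; reporting error has an SD of 0.5 to 1.0 points; and mean reporting error differs between arms by 0 to 0.5 points.

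**The plan's own figure.** 133 vs 39 patients, difference 0.97, SD 1.64, two-sided 5%:
- SE = 1.64 × √(1/133 + 1/39) = 0.299, and 0.97/0.299 = 3.25.
- Power is 90.1% by the normal approximation and 89.8% by the t-test, which matches the stated 90%.
- 39/0.8 = 48.75, rounded up to 49, as stated.

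**How many values can be self-reported?** The record already holds 133 of 167, and 167 − 133 = 34 (20.4%).
- If 134 are analysed in that arm (167 × 0.8), at most 1 is not from the record: 1/134 = 0.7%.
- A share of 20.4% requires all 34 to self-report and none to be missing, so that 167 are analysed.
- The 34 also include dropouts and possibly patients not yet due, since recruitment ran to July 2023. The share is therefore a ceiling.

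**Primary contrast, random error, at the ceiling.** Half-width = 1.96 × SD × √(2/n).
- No reporting error, n = 167: 1.96 × 1.64 × √(2/167) = 0.352.
- Error SD 0.5: SD = √(1.64² + 0.2036 × 0.5²) = 1.655; half-width 0.355 (0.9% wider).
- Error SD 1.0: SD = √(1.64² + 0.2036 × 1.0²) = 1.701; half-width 0.365 (3.7% wider).
- Documented values only, n = 133: 1.96 × 1.64 × √(2/133) = 0.394 (12% wider than 0.352).

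So keeping the self-reports is more precise than dropping them. The two are equal when (1.64² + 0.2036 s²)/167 = 1.64²/133, which gives s = 1.84. Reporting error would need an SD above 1.8 A1C points before exclusion gained precision.

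**Contrasts with attention control (exploratory), differential error.** Bias = share × difference in mean error.
- Ceiling, difference 0.5: 0.2036 × 0.5 = 0.10. SE = 1.64 × √(2/167) = 0.179, ratio 0.567, and the nominal 5% test rejects 8.8% of the time under no effect.
- Ceiling, difference 0.25: bias 0.05, rejection 5.9%.
- One value in 134, difference 0.5: bias 0.004, rejection 5.0%.

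**Usual-care comparison.** The 133 record values against 134 usual-care patients (167 × 0.8) give 99.8% power for 0.97. Self-reports are not needed there, and the sizing does not use them.

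**The case for a change.** The strongest case for a change is that it is cheap and that the share is unknown. A source field, a table by arm and one documented-only analysis would settle the matter. The plan itself keeps such sources apart elsewhere: Table 1 lists self-reported hypoglycemia and medically assisted hypoglycemia as separate outcomes, and the interim analysis in Section C names A1C apart from self-reported data. Blinding in a behavioural trial is imperfect, and it does not turn a recalled figure into a laboratory result.

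Much of this stands. Reporting A1C source by arm is good practice, and so is a documented-only analysis beside the main one. But neither needs an amendment. Record values and survey values arrive by different routes, so their source should be recoverable from the data. A documented-only run treats the other values as missing, which the planned imputation can already handle.

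A formal addition would also gain little standing. The protocol text is dated September 2024, an interim look at A1C was scheduled for March 2024, and an arm-level A1C change is already printed in the plan. An analysis added now could be specified blind to arm, but it could not be called fully prespecified.

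On the usual-care comparison, the plan does not say in words that self-reports are kept out. Its sizing on record values and its retrospective comparator both point to documented values on each side, which is how an analyst would sensibly read it.

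**Conclusion.** The gap exists: undocumented A1C values can enter the primary outcome, and no planned analysis separates them. It is missing detail that analysts can fill sensibly, and the plan as written still supports a sound primary conclusion.

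- **Primary contrast.** No arm-differential error is shown. The MDG+CRx arm is described thus: "Subjects will receive the same intervention above as well as receive vetted, personalized referrals". Section H keeps participants unaware of allocation and the data analyst blinded. Random error widens the interval by at most 3.7% at the ceiling share.
- **Exploratory contrasts with attention control.** A bias of 0.10 and a rejection rate of 8.8% require every patient without a record value to self-report and a half-point difference in mean error between arms. The plan claims no type I error control for these contrasts.
- **Alternative rule.** Excluding self-reports from the main analysis would widen the interval by about 12% at the ceiling share and selectively lose outside-care patients. Keeping them is a fair trade-off.

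These sizes rest on an SD of 1.64 and on attention-control record coverage holding in the other arms; the documents give no figures for those arms. The conclusion would weaken if many more values were undocumented in the MDG arms, or if their share or error differed clearly between MDG and MDG+CRx.
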